6.5.5 Objective physical examination and measurement of vital signs

Objective examination includes auscultation of the heart and lungs, examination of the skin and mucous membranes, palpation of the abdomen, measurement of heart rate, blood pressure and body temperature, as well as other methods of physical examination according to the current clinical situation. Data on changes recorded during the survey are entered in the primary documentation and CRF.

Measurements of heart rate, respiratory rate, blood pressure, body temperature are made at rest (after 15 minutes of rest, not earlier than one hour after smoking cigarettes and 2 hours after eating). Heart rate (HR) is measured by auscultation of the heart in parallel with the determination of pulse rate in the radial artery (or carotid artery with weak pulsation in the radial artery) for one minute in a sitting position, in case of pulse deficit both parameters are recorded: heart rate and pulse rate. Respiratory rate (RR) is measured for a minute at rest in a supine position, noting the respiratory movements of the chest or abdominal wall, without attracting the attention of the patient.

Blood pressure will be measured on the brachial artery in the supine position according to the Korotkov method using a certified sphygmomanometer or tonometer using a cuff length and width selected by the length and circumference of the patient's shoulder. The size of the cuff should correspond to the size of the hand: the rubber part of the cuff should cover at least 80% of the circumference of the shoulder; for adults a cuff 12-13 cm wide and 30-35 cm long (medium size) is used; but it is necessary to have a large and a small cuff for full and thin arms, respectively. The mercury column or tonometer needle must be at the zero mark before the start of the measurement. To assess the level of blood pressure on each arm should perform at least two measurements with an interval of at least 1 min; with a blood pressure difference ≥ 5 mmHg perform one additional measurement; the minimum of three dimensions is taken as the final (registered) value.

Measurement technique:

- Quickly pump air into the cuff to a pressure level 20 mmHg higher than systolic pressure (after the pulse disappears);
- Blood pressure is measured with an accuracy of 2 mmHg;
- Reduce the cuff pressure at a rate of approximately 2 mm Hg in 1 second;
- The level of pressure at which the 1st tone appears corresponds to systolic pressure (1 phase of Korotkov tones);
- The level of pressure at which the disappearance of tones (phase 5 Korotkov tones) corresponds to diastolic pressure; in children, adolescents and young people immediately after exercise, in some pathological conditions in adults, when it is impossible to determine the 5th phase, you should try to determine the 4th phase of Korotkov tones, which is characterized by a significant weakening of tones;

| Bioven | Page 48 |
|----------------------------|--------------------------------|
| Trial Code: 2021-BV-ITP-BP | Version 1.4 from July 03, 2023 |

- If the tones are very weak, you should raise your hand and perform a few compressive movements with a brush, then repeat the measurement, without squeezing the artery with the membrane of the phonendoscope;
- At the initial examination of the patient, the pressure on both arms should be measured; further measurements are performed on the hand on which the blood pressure is higher. Temperature measurements are performed in the axilla using a medical thermometer (thermometer), and the end of the thermometer after shaking should be tightly pressed to her shoulder; the skin of the axilla should be dry, because with wet skin the thermometer shows a lower temperature. The thermometer is kept for 10-15 minutes (the lower the temperature, the longer the column of mercury reaches a peak). The patient should remain completely calm.

Auscultation of the lungs and heart, palpation of the abdomen and examination of the skin and mucous membranes are carried out according to standard procedures adopted in clinical practice at the screening stage, considering the general serious condition of patients. The task of these procedures is to detect pathological changes, including clinically significant. During the observation period, a physically less burdensome set of procedures is performed according to the standard procedure adopted in clinical practice, which allows to assess the patient's condition.

An examination for hemorrhagic syndrome is required. The scale of assessment of severity according to Table 1.

Table.1 Assessment of the severity of hemorrhagic syndrome

| No signs of bleeding | No | | |
|--|--------|--|--|
| Several petechiae (<100 in total) and / or <5 small ecchymoses (<3 cm in diameter, | Mild | | |
| without mucosal bleeding) | | | |
| Multiple petechiae (100 and more) and / or 5 large ecchymoses, 3 cm in diameter, | | | |
| no bleeding of mucous membranes | | | |
| Multiple bleeding of mucous membranes, bleeding gums, menorrhagia, | Severe | | |
| gastrointestinal bleeding | | | |

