In case of any adverse reaction in is necessary to either decrease infusion rate or stop infusion. Treatment required depends on the nature and severity of adverse reaction. In case of a shock measures should be taken in accordance with approved recommendations on anti-shock therapy.

For all patients in case of IgG administration it is necessary to:

perform an adequate hydration before starting IgG infusion;

- monitor diuresis;
- monitor blood serum creatinine level;
- avoid a concomitant use of loop diuretics.

Overdose.

Overdose can cause hypervolemia and increase of blood viscosity especially in patients with such risks including older patients or patients with renal impairment.

Adverse reactions.

Blood and lymphatic system disorders: anemia, lymphadenopathy, hemolysis, leukopenia, hemolytic anemia.

Immune system disorders: hypersensibility, anaphylactic shock, anaphylactic reactions, anaphylactoid reactions, angioneurotic edema, facial edema.

Endocrine system disorders: abnormality of thyroid function.

Nervous system disorders: headache, disorder of cerebral circulation, aseptic meningitis, migraine, dizziness, paresthesia, hyposthesia, amnesia, burning sensation, dysarthria, dysgeusia, balance disorders, transient ischemic attack, tremor.

Psychiatric disorders: excitation, anxiety, insomnia.

Cardiac disorders: myocardial infarction, tachycardia, palpilation, cyanosis.

Vascular disorders: peripheral vascular failure, arterial hypotension, arterial hypertension, peripheral coldness, phlebitis, deep venous thrombosis.

Respiratory, thoracic and mediastinal disorders: respiratory failure, pulmonary embolism, pulmonary edema, bronchial spasm, dyspnea, cough, increased respiratory rate, rhinorrhea, asthma, nasal blockage, oropharyngeal edema, pharyngolaryngeal pain.

Gastrointestinal disorders: nausea, vomiting, diarrhea, abdominal pain.

Skin and subcutaneous tissue disorders: eczema, urticaria, rash, erythematous rash, dermatitis, pruritus, alopecia, cold sweat, photosensitivity reactions, night sweating.

Musculoskeletal and connective tissue disorders: back pain, pain in extremities, arthralgia, muscle spasm, clonus, myalgia.

Renal and urinary disorders: acute renal failure, proteinuria.

Eye disorders: conjunctivitis, eye pain, eye edema.

Ear and labyrinth disorders: vertigo, liquid in internal ear.

| Bioven | Page 35 |
|----------------------------|---------------------------------|

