All screening data are entered into the primary documentation and IRF of patients. The researcher checks the patient's compliance with the inclusion/exclusion (exclusion) criteria and decides on possible participation in the clinical trial. Due to the variability in PLT levels in patients with chronic immune thrombocytopenia (wave-like), it is possible to re-screen or extend the duration of the screening stage, but only if the study subject meets all other specified inclusion criteria, does not have non-inclusion and exclusion criteria.

Visit 2. (Day 0, Day +1, Day +2): Study Drug administration within 2 days. Observation.

Content of the visit:

The patient is hospitalized for 3 days for the introduction of the Study Drug (SD).

- 15 minutes before the start of each SD administration and after drug administration, a
 physical exploring is performed: determination of the dynamics of the hemorrhagic
 syndrome (exploring of the skin and mucous membranes, the presence / absence of
 bleeding); palpation and percussion of the abdominal organs; auscultation and percussion of
 the heart and lungs; Measurement of vital signs (body temperature, heart rate, blood pressure,
 respiratory rate);
- Administration of SD for 2 consecutive days at a dose of 0.8-1.0 g/kg per day (course dose 1.6-2.0 g/kg);
- After 48 hours (+/- 2 hours) from the beginning of the first SD administration, a blood sample is taken for general blood test, biochemical blood test, Coombs' test and Ig G level according to the "Schedule of Procedures";
- AE/AR registration;
- Discharge of the patient and appointment of the date of the next visit.

Visit 3 (Day +7 ± 1 day): Observations.

The patient is:

- Physical exploring is performed: determination of the dynamics of the hemorrhagic syndrome (exploring of the skin and mucous membranes, the presence / absence of bleeding); palpation and percussion of the abdominal organs; auscultation and percussion of the heart and lungs;
- Measurement of vital signs (body temperature, heart rate, blood pressure, respiratory rate);
- General blood test: hemoglobin, hematocrit, erythrocytes, leukocytes, platelet count according to Fonio;
- Coombs' test is performed in case of hemolysis according to the laboratory test at the previous visit;
- Determination of total IgG in serum (g/l);
- Rating according to the exclusion criteria;
- AE/AR registration;
- Discharge of the patient and appointment of the date of the next visit.

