9 SECURITY ASSESSMENT

9.1 Security endpoints

- Frequency of side effects;
- Frequency of serious side effects;
- Frequency of clinically significant changes in laboratory parameters and vital signs after infusion of the study drug;
- Dynamics of laboratory parameters.

9.2 Definitions concerning safety assessment.

Adverse event

Adverse event (AE) is any adverse change in the health of a patient or subject who has been administered a drug, regardless of the causal relationship with its use.

AE can be any adverse and unintentional change, symptom or disease, the time of occurrence of which does not exclude a causal relationship with the use of the drug, regardless of the presence or absence of a relationship with the use of the drug.

AEs may be abnormal laboratory parameters, first-time symptoms, or diseases that are related to the use of the drug, or if they existed before treatment of a condition whose severity or frequency increased after administration of the study drug.

Any medical condition present at the time of the patient's screening, but not deteriorating during the study, should not be recorded as an AE. However, if this medical condition worsens at any time during the study, it should be recorded as an AE.

Medical interventions, such as surgeries, diagnostic and treatment procedures, are not AEs, but they are interventions to treat the relevant medical condition and should be registered as a treatment for ANs.

Deviations from the norm of laboratory parameters

Any deviation from the norm of the laboratory indicator, which appeared for the first time, or the degree of severity, the frequency of which has increased compared to baseline, and meets at least one of the following criteria, must be recorded as AE:

- Requires medical intervention or diagnostic procedure;

- Leads to the cancellation of the study drug;
- Accompanied by complaints or symptoms, or causes them;
- Considered by the researcher as "clinically significant".

If there is any doubt as to whether a clinical event is an AE, it should be recorded as an AE.

Adverse reaction

Adverse reaction (AR) is an adverse reaction of the body associated with the use of a medicinal product (study drug), which implies the presence of at least a possible relationship with the use of a suspected drug (study drug).

During the study period, the investigator or study staff should conduct surveys and record information on adverse events / reactions as defined in this section of the protocol.

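### Section 6.5.5 registers the lowest of three blood pressure readings when the first two disagree, which biases recorded levels low and adds noise to before/after changes; one averaging rule would remove this.

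*Combined protocol and SAP*

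**What the plan says.** Section 6.5.5 sets the measurement rule. For each arm the investigator "should perform at least two measurements with an interval of at least 1 min". If those two values are 5 mmHg or more apart, a third reading follows. The text then fixes what goes into the record in that case: "the minimum of three dimensions is taken as the final (registered) value". The section does not state which value is registered when the first two readings differ by less than 5 mmHg. No other section changes the rule or limits it to one visit.

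The same section sets the conditions: "Measurements of heart rate, respiratory rate, blood pressure, body temperature are made at rest". The patient must have rested for a quarter of an hour beforehand. On the choice of arm after the initial examination, it says that "further measurements are performed on the hand on which the blood pressure is higher".

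Section 6.6 (Visit 2) times the vital signs "15 minutes before the start of each SD administration and after drug administration", and the synopsis also asks for blood pressure during each administration. Section 9.1 lists as a safety endpoint "Frequency of clinically significant changes in laboratory parameters and vital signs after infusion of the study drug". Section 10.3.4 summarises blood pressure descriptively by visit and asks for its trend. The adverse reactions listed in section 2.4 include "Vascular disorders: peripheral vascular failure, arterial hypotension, arterial hypertension".

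**The concern.** The lowest of three readings is not a neutral summary of a patient's pressure: its expected value lies below the true value, and further below it the more the readings scatter. Here it applies only when readings disagree. One CRF field therefore holds two different statistics, and one of them is not defined in the text.

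At stake is the accuracy of the blood pressure values behind the vital-signs endpoint and the by-visit summaries. The trial has a single arm, so no concurrent group carries the same bias and absolute levels have to be read on their own. The listed reactions include both raised and lowered pressure, so a rule that shifts values downward affects both: fewer borderline high values and more borderline low ones.

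**Working it through.** The plan states no figure for this point, so there is nothing to reproduce. The check simulates the rule as written.

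**Inputs from the documents (6.5.5):** two readings; a third if |x1 − x2| ≥ 5 mmHg; the minimum of the three is then registered.

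**Assumptions, not in the documents:**
- Readings are independent and normal around a stable true value, with within-session SD s of 2 to 8 mmHg.
- When no third reading is taken, the mean of the two is registered.
- The comparator registers the mean of three when a third is taken.

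**Step 1: how often the third reading is triggered.** The difference x1 − x2 has SD s√2, so P(trigger) = 2 × [1 − Φ(5 / (s√2))]. At s = 5 this is 2 × [1 − Φ(0.707)] = 0.48.

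**Step 2: bias in the registered level.** Sessions without a third reading are unbiased under the assumption above, so overall bias = P(trigger) × bias in triggered sessions. At s = 5 this is 0.48 × (−5.46) = −2.6 mmHg. Results from at least 1,000,000 simulated sessions per setting:

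| s (mmHg) | Third reading taken | Bias when taken | Bias over all sessions | Bias if the mean is registered |
|---|---|---|---|---|
| 2 | 8% | −3.2 | −0.2 | 0.0 |
| 3 | 24% | −3.9 | −0.9 | 0.0 |
| 5 | 48% | −5.5 | −2.6 | 0.0 |
| 8 | 66% | −7.9 | −5.2 | 0.0 |

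**Step 3: values near a cut-off (s = 5).** The documents give no numeric threshold, so 140 and 90 mmHg are illustrations only.
- True 145: P(registered ≥ 140) is 0.70 under the minimum rule, against 0.94 with the mean.
- True 150: 0.95 against 1.00. True 160: 1.00 under both.
- True 92: P(registered < 90) is 0.55 under the minimum rule, against 0.27 with the mean.

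**Step 4: change from before to after infusion.** Write b0 and b1 for the size of the low bias before and after. Registered change = true change − (b1 − b0).
- *Equal variability:* b1 = b0, so a true rise of 20 mmHg registers as 20.0 on average at every SD tried.
- *Noise:* at s = 5 the SD of one registered value is about 4.50 under the minimum rule and 3.24 with the mean. Multiplying by √2 gives an SD of the change of about 6.4 against 4.6 mmHg.
- *Effect of that noise (s = 5, illustrative cut-off of 20 mmHg):* P(recorded change ≥ 20) falls from 0.86 to 0.78 for a true rise of 25, but increases from 0.14 to 0.22 for a true rise of 15.
- *More variable readings after infusion, SD 3 to 5:* 20 − (2.62 − 0.93) = 18.3.
- *More variable readings after infusion, SD 3 to 8:* 20 − (5.20 − 0.93) = 15.7.

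**The case against.** The strongest reply is that the endpoint concerns change after infusion, and the same rule applies on both sides of it. With equal variability the bias cancels in the mean change, as Step 4 shows. This stands. What remains of the problem for change is extra noise, which misclassifies in both directions.

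A reader might go further and infer that the rule conceals infusion-related hypertension. The documents do not support that. It would need pressure readings to be less stable after infusion than before, and no section says so; the requirement for rest before measurement works against it. Even if variability did increase, rises would be attenuated, not lost. The 140 mmHg illustration concerns a level close to a cut-off that the plan does not contain, and clearly raised values register under either rule.

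There are also safeguards. Later readings use the arm with the higher pressure, the synopsis asks for blood pressure during administration, and section 9.3 requires adverse events to be registered whatever their severity or causality. These soften the effect. They do not correct the registered numbers: choosing the higher arm selects the limb, and the minimum is still taken within it; adverse event reports do not alter the values summarised under 10.3.4.

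Finally, the size rests on an undocumented SD. At SD 2 the overall bias is only 0.2 mmHg. That is a fair limit on the magnitude, but not on the direction.

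**Conclusion.** Wrong as written, and minor. The text of 6.5.5 is clear that the minimum is registered when a third reading is taken, and it leaves the other case undefined. Absolute levels are biased low by 0.2 to 5.2 mmHg overall for an assumed within-session SD of 2 to 8 mmHg (2.6 at SD 5), given the further assumption that the mean of two is registered when the readings agree. The direction is certain; the size is not.

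For change across an infusion there is no average bias if variability is equal at both times, only a wider spread (about 6.4 instead of 4.6 mmHg at SD 5). Rises are attenuated only if readings become more variable afterwards, which the documents neither state nor exclude. Blood pressure is a descriptive safety variable here, so the primary endpoint, the sample size and the non-inferiority conclusion are untouched.

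**What to change.** In section 6.5.5, register the mean of the readings taken: two, or three when the first two differ by 5 mmHg or more. Apply that rule at every assessment, including those before, during and after each infusion, and record the individual readings in the CRF. This also settles the undefined case. If "minimum" is a translation slip, the sentence still needs correcting, because sites will follow it as printed.

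The cost is one sentence in the protocol and the matching CRF instruction, plus fields for the individual readings if the CRF does not already hold them. No extra measurement is needed.

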6.5.6 Bioanalytical procedures and laboratory tests

Blood and urine are taken as biomaterial.

The procedure for taking biomaterial for laboratory analysis is carried out at the study site or at the collection point (if the investigator thinks the patient is mobile), or by the visiting team of the Central Laboratory designated by the Sponsor.

Blood samples for analysis will be taken on an empty stomach (8-10 hours after the last meal) from a vein with a disposable sterile syringe, catheter, or vacutainer under aseptic / antiseptic conditions.

The amount of blood taken is determined by the list of laboratory tests that need to be performed.

For the general analysis of urine, the morning average portion after adequate hygiene of a perineum is collected, urine must be delivered to laboratory within two hours after collecting.

Blood tests for HIV, blood samples for clinical blood tests, biochemical blood tests, urine samples for general analysis, inflammatory markers are selected according to standard procedures according to laboratory guidelines, according to the "Schedule of study procedures" (Table 1, Section 6.4).

List of laboratory tests:

- blood test for HIV, RW, HBs-Ag, anti-HCV (virological screening), PCR CMV, EBV or primary documentation data;
- general blood test (erythrocytes, hemoglobin, platelet counting by the Fonio method, leukocytes and leukocyte formula, reticulocytes with low hemoglobin, but not less than 90 g / l);
- biochemical blood test (ALT, AST, creatinine, urea, glucose, total bilirubin);
- Coombs' test (antiglobulin test);
- determination of the level of total IgG g / l in serum;
- antinuclear antibodies (AHA);
- general analysis of urine (color, transparency, specific gravity, pH, glucose, protein, ketone bodies, sediment microscopy (erythrocytes, leukocytes, cylinders, crystals, bacteria / fungi);
- pregnancy test for women of reproductive age.

6.5.7 Bioanalytical study plan

Bioanalytical research procedures will be conducted in a certified laboratory designated by the Sponsor of the study, whose activities are organized in accordance with the requirements of Good Clinical Practice - GSP.

All plasma and serum samples, as well as the blood itself, including samples obtained from patients who did not pass the study in full (prematurely dropped out of the study) are subject to bioanalytical tests.

Examination of samples that have not been subjected to freezing is carried out according to standard methods by routine methods of biochemical and hematological analysis.

Defrosting of plasma samples should be performed at room temperature.

6.5.8 Validation of bioanalytical methods

The bioanalytical method used must be properly validated and documented in accordance with GSP standards and regulatory requirements during the study period.

The main purpose of validation is to prove the reliability of this method for quantifying the concentration of the analyte in serum.

Validation is carried out considering the main criteria for the acceptability of the bioanalytical method set out in the guidelines.

The following characteristics of the bioanalytical method should be evaluated during the validation process:

1) selectivity;

- 2) transfer of the sample;
- 3) lower limit of quantification;
- 4) the range of concentrations to be determined and the shape of the calibration curve;
- 5) correctness;
- 6) precision;
- 7) extraction degree;
- 8) stability of the basic and working solutions of the analyte, stability of the analyte in the biomaterial (blood serum) under processing conditions and throughout the storage period (post-preparation stability; short-term temperature stability, stability after freezing / thawing; long-term stability).

Validation of each bioanalytical method should consist of two separate phases:

| Bioven | Page 50 |
|----------------------------|--------------------------------|
| Trial Code: 2021-BV-ITP-BP | Version 1.4 from July 03, 2023 |

- phase preceding the study, during which the compliance of the method of quantification of the above characteristics is checked;
- 2) phase of the study itself, during which the validated bioanalytical method is checked for compliance with the obtained results to the criteria of acceptability - to decide on the acceptance of the results of analytical runs in the routine analysis of biosamples.

The results and progress of the validation should be presented in the validation report (for the first phase of validation) and in the Analytical report (for the second phase of validation), prepared by the laboratory involved in the study.

6.5.9 Test tube labeling procedure.

The procedure for taking biomaterial for laboratory analysis is carried out at the collection point (if the investigator thinks the patient is mobile) or by the visiting team of the Central Laboratory designated by the Sponsor.

In case of taking biomaterial not at the point of collection, blood sampling tubes, plasma vacutainers are pre-labeled. Markings are applied by the printer on labels and protected with an adhesive tape.

